#### 4.6.1 Primary Efficacy Endpoints

For PTPs, there is no primary efficacy endpoint. Efficacy endpoints for PTPs are described in Section 4.6.2 (Secondary Efficacy Endpoints).

The primary efficacy endpoints for PUPs are:

- Treatment success for major bleeding episodes, defined as a rating of "excellent" or "good" on the investigator's clinical assessment of hemostatic efficacy 4-point scale.
- Annualized spontaneous Bleeding Rate (AsBR)

##### 4.6.1.1 Method of Analysis for the Primary Efficacy Endpoint

The primary endpoint will be summarized for the Efficacy population as described in [Section 4.1](#).

#### Arm 1 and Arm 3 (PTPs)

There is no primary efficacy endpoint.

#### Arm 2 (PUPs)

##### Treatment success for major bleeding episodes

The number of bleeds and the number of treated bleeds will be presented. The percentage of bleeds treated successfully will be reported with a 95% CI. To estimate this percentage, the numerator will include the number of bleeding episodes treated with rVIII-SingleChain and rated as "excellent" or "good" (See Table 6 in Section 8.4.1 of the clinical protocol for details); and the denominator will include all treated bleeding episodes. Missing assessment will be counted as failures. With this approach, the following treated bleeds will be considered treatment failures in the primary analysis: those with ratings of "moderate", or "poor/none"; those treated with products other than rVIII-SingleChain regardless of the assessment; and those with missing investigator ratings. In order to account for within-subject correlation, generalized linear modeling using SAS' GENMOD procedure will be utilized. The model will contain only the intercept term. The binomial distribution with logit link function will be specified.

Two sensitivity analyses of the primary endpoint will be performed:

- In the first sensitivity analysis, missing investigator ratings will be excluded from the denominator.
- In the second sensitivity analysis, missing investigator ratings will be counted as treatment successes.

Results will be presented overall and by treatment modality.

Only bleeding episodes classified as major will be included in this analysis. Bleeding episodes reported by the subject in the eDiary will be excluded since major/minor classification is not collected.

Major and minor bleeds by inhibitor status will be summarized for PUPs.

CCI

Summary of rVIII-SingleChain treated bleeding events will be listed while inhibitor positive and per patient.

rVIII-SingleChain Non-Inhibitory Anti-Drug Antibodies, patient related risk factor, treatment related risk factor will be listed for PUPs.

Treatment related risk factor and patient related risk factor will be summarized by inhibitor group.

Bleeding events not treated with rVIII-SingleChain will be listed for PUPs.

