7.1 Contraindications and Precautions to Further Dosing

If the subject experiences a hypersensitivity reaction, the study treatment must be stopped immediately by discontinuation of the injection and the medical monitor must be contacted before the administration of additional doses of rVIII-SingleChain.

High-titer inhibitor in Arm 2 (PUPs): If a subject in Arm 2 (PUPs) develops a high-titer inhibitor (confirmed by repeat testing at the central laboratory), no further on-demand or prophylaxis doses of rVIII-SingleChain must be administered to this subject until subject eligibility for the CCI substudy has been confirmed and the subject is enrolled in the CCI substudy (see [Appendix 1](#)), unless deemed necessary by the investigator.

Low-titer inhibitor in Arm 2 (PUPs): If a subject in Arm 2 (PUPs) develops a low-titer inhibitor (confirmed by repeat testing at the central laboratory), the following options apply, at the discretion of the investigator after discussion with the sponsor:

- The investigator may decide to enroll the subject into the CCI substudy (see [Appendix 1](#)).
- The subject may continue in the main study.

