11.2.3 Efficacy Population

The efficacy population will consist of all subjects in the safety population who receive at least 1 dose of rVIII-SingleChain as part of either routine prophylaxis treatment or on-demand treatment during the study. Additionally, the efficacy population will only include subjects who do not have an inhibitor.

The Efficacy population might be the same as the Safety population.

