11.3.2.1 Primary Efficacy Analysis

For **Arms 1 and 3 (PTPs)**, there is no primary efficacy endpoint.

For **Arm 2 (PUPs)**, the analyses of the primary efficacy endpoints are outlined below:

- The investigator's clinical assessment of hemostatic efficacy for the treatment of **major** bleeding episodes, based on the 4-point ordinal scale (excellent, good, moderate, poor / no response), will be tabulated. The percentage of major bleeding episodes treated successfully (defined as ratings of excellent or good) will be summarized, and reported together with a two-sided 95% CI. To estimate the proportion, the denominator will include all treated bleeding episodes categorized as major. To account for within-subject correlation, generalized linear modeling using SAS' GENMOD procedure will be utilized. The model will contain only the intercept term. The binomial distribution with logit link function will be specified.
- The AsBR will be derived for each subject as follows: ((number of spontaneous bleeding episodes) / (observed treatment period of interest))*365.25. The AsBR will be summarized by regimen (on-demand or prophylaxis) using descriptive statistics. In addition, the number of spontaneous bleeding episodes per year and associated 95% CI will be estimated based on a Poisson model. Generalized linear modeling using SAS' GENMOD procedure will be utilized. The Poisson distribution with log link function, and log_time offset will be specified. The Poisson-based number of spontaneous bleeding episodes per year will be presented by regimen (on-demand or prophylaxis).

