## 4.6 Efficacy Analysis

The efficacy endpoints will be summarized and analyzed for the Efficacy population unless otherwise specified. The surgery substudy efficacy data will be summarized for the Surgery population. Efficacy analyses will be performed separately for the PTPs and PUPs and by modality. Efficacy results for the PUPs will be presented by inhibitor status (positive, negative) and overall.

The efficacy evaluation period begins on Treatment Day 1 date in this study and ends at the End of study Visit in this study or the last date of dose, whichever occurs later. Only those treated bleeding episodes and doses which fall within the efficacy evaluation period will count

towards the efficacy evaluation. The summary statistics to be presented are described in [Section 4.1](#).

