## 4.11 Changes in Conduct or Planned Analyses from the Protocol

Section 2.1 and 2.2: In the protocol, incidence of inhibitor formation to FVIII in Arm 2, PUPs is stated that would be performed on at least 50 PUPs. However, this condition has been removed. Given that patients that develop inhibitors may be withdrawn from the study early, they would not necessarily achieve 50 exposure days but we would definitely have to include them in the calculation. Therefore the text was adjusted to ensure the option to properly report the endpoint regardless of these circumstances.

CCI

Section 3.5.3: Efficacy Population definition has been changed removing the exclusive inclusion of subjects who do not have an inhibitor at any time point during the study.

CCI

Section 4.6.1 and 4.6.2.1: In the Annualized Bleeding Rate analysis it has been added that subjects with an efficacy evaluation period less than 8 weeks (56 days) will be excluded from the analysis to exclude bias due to short evaluation period.

Section 4.6.2.2: The analysis of number of infusions of CSL627 required to achieve hemostasis has been added for completeness of analysis.

Section 4.7.1: Incidence of transient inhibitors has been added for completeness of analysis.

Section 4.7.2.1: Analysis of AESIs has been added for completeness of analysis.

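### Arm 2 major bleeds treated only with a bypassing agent count as rVIII-SingleChain failures in the overall success rate, and neither sensitivity analysis removes them

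*SAP*

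**What the plan says.** Treatment success for major bleeds is a primary efficacy endpoint in Arm 2.

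- **Denominator.** Protocol 11.3.2.1 says "the denominator will include all treated bleeding episodes categorized as major". SAP 4.6.1.1 agrees: "the denominator will include all treated bleeding episodes", with only major bleeds entering.
- **Failure rule.** The protocol defines success by the investigator's rating alone. SAP 4.6.1.1 adds further failures: missing ratings, and "those treated with products other than rVIII-SingleChain regardless of the assessment". The visible text of SAP 4.11, which lists departures from the protocol, does not mention the other-product rule.
- **Population.** Protocol 11.2.3 states that "the efficacy population will only include subjects who do not have an inhibitor". SAP 3.5.3 has no such restriction, and SAP 4.11 declares the change: "Efficacy Population definition has been changed removing the exclusive inclusion of subjects who do not have an inhibitor".
- **Time window.** SAP 4.6: "The efficacy evaluation period begins on Treatment Day 1 date in this study and ends at the End of study Visit in this study", or at the last dose if later. The visible text takes no inhibitor-positive time out of this window.
- **Treatment in inhibitor subjects.** Protocol 5.5 and 7.2 permit bypassing agents in subjects with inhibitors. For a confirmed high-titer inhibitor in Arm 2, Protocol 7.1 adds that "no further on-demand or prophylaxis doses of rVIII-SingleChain must be administered to this subject" until enrollment in the substudy, unless the investigator judges it necessary. A PUP with a low-titer inhibitor may stay in the main study, and no withholding rule is stated.
- **Displays.** SAP 3.5.6 and 4.6 present PUP hemostatic efficacy by inhibitor status as well as overall. SAP 4.6.1.1 adds results by modality and a listing of PUP bleeds not treated with rVIII-SingleChain. Its two sensitivity analyses vary only the handling of missing ratings.

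**The concern.** Each rule is defensible alone. Scoring a switch to another product as failure is a common conservative choice, and while inhibitor subjects were outside the Efficacy population it would rarely have met a bypass-only bleed. Once the SAP brought those subjects in, the same rule began to score bleeds in which rVIII-SingleChain was never tried.

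Such a bleed cannot count as a success whatever happens clinically. It carries no information on the product's hemostatic effect. It records that the child had an inhibitor and was treated with something else, and high-titer inhibitor incidence is already a separate primary endpoint in Arm 2. The overall rate would then blend two primary questions, and a reader could not tell how much of a low figure came from each.

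The protocol follows a different logic for surgery. Protocol 3.5 and 8.5 keep inhibitor-positive PUPs out of the surgery substudy because their procedures would be covered by a bypassing agent.

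**Working it through.** **1. Is there a figure in the plan to reproduce?** No. Protocol 11.1 gives no sample size calculation, and neither document states an expected success rate or number of major bleeds.

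**2. Tracing one bleed through the rules.** Take a major bleed in a PUP with a confirmed inhibitor, treated only with a bypassing agent.

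- It is treated and major, so it is in the denominator.
- The child received rVIII-SingleChain earlier, so he is in the SAP's Efficacy population. Under Protocol 11.2.3 he would not be.
- It falls within the efficacy evaluation period.
- It was treated with another product, so it is a failure whatever the rating.

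Protocol 4.2.1 withdraws PUPs who use another FVIII product. For those who stay on study, other products are therefore largely bypassing agents, or plasma or cryoprecipitate.

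**3. Which displays are affected?** SAP 3.5.6 runs the inhibitor-positive period from after the first positive titer, later confirmed, to confirmed eradication. Bleeds arising under the Protocol 7.1 hold fall in that period. The inhibitor-positive, overall and by-modality rates carry them; the inhibitor-negative rate largely does not.

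**4. Are such bleeds plausible?** Protocol 1.1 cites a 35.4% cumulative inhibitor incidence within 50 exposure days, and Protocol 11.1 targets 24 PUPs: 24 × 0.354 = 8.5 children with an inhibitor of any titer. The figure comes from another cohort, and Arm 2 excludes a first-order family history of inhibitors, so it shows plausibility only. It does not give a count of bypass-only major bleeds.

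**5. Size, on assumed counts.** Let M be major bleeds given at least one dose of rVIII-SingleChain, S the successes among them, and B the bypass-only major bleeds.

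- SAP rule: S / (M + B)
- Product-treated version: S / M
- Ratio of the first to the second: M / (M + B)

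M, S and B are all assumptions. Intervals are Clopper-Pearson 95% and ignore within-subject correlation, unlike the planned model.

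| Assumed S/M | B = 0 (equals S/M) | B = 1 | B = 2 | B = 5 |
|---|---|---|---|---|
| 5/5 | 100.0% (47.8–100.0) | 5/6 = 83.3% | 5/7 = 71.4% | 5/10 = 50.0% (18.7–81.3) |
| 9/10 | 90.0% (55.5–99.7) | 9/11 = 81.8% | 9/12 = 75.0% | 9/15 = 60.0% (32.3–83.7) |
| 18/20 | 90.0% (68.3–98.8) | 18/21 = 85.7% | 18/22 = 81.8% | 18/25 = 72.0% (50.6–87.9) |

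The effect depends on B relative to M. M may well be small: major bleeds are those threatening life or limb (Protocol 8.3.2), and SAP 4.6.1.1 leaves eDiary-reported bleeds out of this analysis.

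**6. A gap in the sensitivity analyses.** Protocol 8.4.1 asks the investigator to rate the hemostatic efficacy of rVIII-SingleChain, so a bypass-only bleed may well go unrated. It then meets both the other-product rule and the missing-rating rule, and the SAP does not say which prevails. Take S/M = 9/10 and B = 2, both unrated, with every other bleed rated:

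- First sensitivity analysis (missing excluded): 9/10 = 90.0% if the missing-rating rule prevails, 9/12 = 75.0% if the other-product rule does.
- Second (missing counted as success): (9 + 2)/12 = 91.7%, or 9/12 = 75.0%.

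On one reading of the second analysis, a bleed that never received the product becomes a success of it.

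**The case against.** The strongest reply is that the plan already deals with most of this. Efficacy in PUPs is shown by inhibitor status, and the inhibitor-negative rate approximates the protocol's inhibitor-free population. Bleeds not treated with the product are listed. The other-product rule is openly conservative, which suits an open-label study with investigator ratings, and the denominator is the protocol's own. There is no success threshold and no p values are planned, so no stated decision turns on the rate. All of this stands. It limits the point to the overall, by-modality and inhibitor-positive rates, and it argues against replacing the main denominator.

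Redaction also limits the point. Much high-titer time may fall in the substudy, and there is redacted text within SAP 4.6.1.1 itself. The visible SAP takes a redacted period out of treatment-emergent adverse events (4.7.2) and local tolerability (4.7.3). It states no such exclusion for this endpoint, but one may exist in text that cannot be seen.

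A reader might infer that the protocol withholds rVIII-SingleChain from every inhibitor-positive PUP, so that each such failure is forced by the protocol. Protocol 7.1 does not support that. The hold covers confirmed high-titer inhibitors only, ends at substudy enrollment and can be overridden by the investigator. Those who decline the substudy must be withdrawn (Protocol 4.2.1). In low-titer PUPs a bypassing agent is permitted, and its use is a clinical choice.

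What the reply leaves open is the headline rate. A listing does not change how a bleed is scored, and no planned analysis shows what the overall rate would be without bypass-only bleeds.

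**Conclusion.** The point holds for the overall, by-modality and inhibitor-positive success rates. Under the visible SAP text, a bypass-only major bleed in an inhibitor-positive PUP lowers these rates without measuring the product's hemostatic efficacy. This follows from the other-product failure rule together with the wider Efficacy population, and neither sensitivity analysis isolates it.

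The size is unknown. Each such bleed multiplies the product-treated rate by M / (M + B). With an assumed 9 of 10, one to five bypass-only bleeds move 90.0% to between 81.8% and 60.0%; with none, nothing changes. The conclusion assumes that some such bleeds occur and that redacted text does not already set them aside.

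A reader might also infer that the endpoint as a whole is invalid, or that the main denominator is an error. The documents support neither. The inhibitor-negative rate remains interpretable, and the all-treated denominator is what Protocol 11.3.2.1 specifies. The defect is one of interpretation in a primary endpoint, and it is cheap to repair.

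**What to change.** 1. Keep the protocol's all-treated denominator, with the present failure rule, as the main analysis.
2. Add a third sensitivity analysis limited to major bleeds that received at least one dose of rVIII-SingleChain. Bleeds that then needed another product stay in it as failures.
3. Tabulate the number of bypass-only major bleeds beside the overall, by-modality and by-inhibitor-status rates.
4. State that the other-product rule takes precedence in the second missing-rating analysis, so that an unrated bypass-only bleed is not turned into a success. Say also how it is handled in the first.
5. Reconcile the Efficacy population in Protocol 11.2.3 with SAP 3.5.3, and add the other-product failure rule to the departures listed in SAP 4.11.

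The cost is SAP wording, one extra analysis and one extra row of counts. The downside is that the added rate is less conservative than the main one, so it should be labelled as a sensitivity result and shown next to the main rate.

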## 4 Statistical Methodology

### 4.1 Planned Analyses

Statistical programming and analyses will be performed by a Contract Research Organization (PPD [REDACTED]) under the supervision of CSL Behring. Data derivations and manipulations and statistical analyses will be performed using SAS® version 9.2 or higher.

All summaries and analyses will be provided separately for PTPs and PUPs. For the separate presentation of PTPs and PUPs, all summaries and analyses will be presented as a total and by assigned treatment modality (prophylaxis, on-demand) and/or by age group for PTPs: 0 to < 6 years, ≥ 6 to < 12 years, ≥ 12 to < 18 years and ≥ 18 to ≤ 65 years, 0 to <12 years, ≥12 to ≤ 65 years.

All continuous variables will be summarized in terms of the observed sample size, mean, standard deviation, median, minimum, and maximum. Other descriptive statistics (e.g., quartiles, coefficient of variation) may be reported when appropriate. All categorical variables will be summarized using frequency counts and percentages.

Unless otherwise specified, Confidence Intervals (CIs) presented will be two-sided 95%.

Number of subjects screened will be reported. Unless otherwise stated, baseline and demographic characteristics will be summarized for the Safety, Efficacy, Surgery and C [REDACTED] populations. Note: If the Safety and Efficacy populations are equal, only the safety population should be produced and a footnote added regarding the efficacy population.

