### AsBR

AsBR will be derived by inhibitor status and overall as follows:

$$(\text{number of bleeding events}) / (\text{observed treatment period of interest days}) * 365.25.$$

Only bleeding events requiring treatment will be included in the derivation of bleeding rates. The AsBR will be estimated for subjects who complete at least 8 weeks of treatment on the given inhibitor status using the subject's observed data. If the subject does not complete at least 8 weeks of treatment on the given inhibitor status, then the AsBR will be considered missing.

The number of spontaneous bleeding episodes per year based on a Poisson model and associated 95% CI and the number and percentage of subjects with zero bleeding episodes will be presented. In addition, the rate ratio of Prophylaxis modality to On-Demand modality (Prophylaxis- On-Demand) will be presented, along with the associated 95% CI, as obtained by the Poisson model.

Spontaneous bleeding episodes are those classified as 'Non-traumatic' in e-Diary or 'Spontaneous' in the eCRF. Annualized spontaneous bleeding rate will also be summarized for the following subgroup:

- Positive non-inhibitory Anti-Drug Antibodies (ADAs) and negative during the study
- Age based on age in this study: for PTPs: 0 to < 6 years,  $\geq 6$  to < 12 years,  $\geq 12$  to < 18 years and  $\geq 18$  to  $\leq 65$  years, 0 to <12 years,  $\geq 12$  to  $\leq 65$  years.
- Prophylaxis frequency: every second day, 3 times per week, 2 times per week, other regimen.

In these subgroup analyses rate ratio of Prophylaxis modality to On-Demand modality won't be displayed.

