#### The transient inhibitor incidence

- Numerators = Number of PUPs subjects who develop inhibitors and have subsequent negative results within 6 months, i.e. 183 days
- Denominators = Total number of PUPs who develop inhibitors

A two-sided 95% exact CI for the incidence of inhibitor formation will be calculated. If zero inhibitors are observed, then a one-sided 97.5% upper confidence limit will be calculated. SAS' FREQ procedure will be applied to produce an exact CI, which uses the Clopper-Pearson CI as the default method, however, Wald CIs will also be presented. The analysis will be performed also by race.

For PUPs, the incidence (with CI) of inhibitor formation to FVIII will be estimated also by Total EDs ranges. According to the Total EDs they were exposed at time of first positive FVIII inhibitor test PUPs will be classified into 0-10 EDs, >10-25 EDs, >25-50 and >50 EDs. Assessments at EDs=0 are defined as those assessments done before date and time or on the same date and time of first dose. If time of assessment or time of first dose is missing then the inhibitor result taken at the same date of the first dose will be considered as at EDs=0. An assessment done on the same date and time of a dose will be considered to be exposed to the number of EDs the subject has been exposed before that date and time. If time is missing for the assessment or the dose, then the assessment done on the same date of dose will be considered to be exposed to the EDs the subject has been exposed before the date of that dose.

Summaries of inhibitors assay test and inhibitor titer while subjects are inhibitor positive will be provided.

The incidence of inhibitor formation to FVIII will be also summarized at the assessment of 10, 50 and 100 EDs in the current study as collected in the eCRF.

Analysis will be performed overall, by region and considering the Japanese subgroup only.

CCI

CCI

CCI

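### The only 95% CI specified for PUP major-bleed treatment success is unusable if all, or none, of the treated major bleeds in a reported cell are successes

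*SAP*

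**What the plan says.** Treatment success for major bleeds is a primary endpoint in Arm 2 (Protocol 2.1.2; SAP 2.1 and 4.6.1). SAP 4.6.1.1 states: "The percentage of bleeds treated successfully will be reported with a 95% CI". Protocol 11.3.2.1 makes that interval two-sided and names the method: "To account for within-subject correlation, generalized linear modeling using SAS' GENMOD procedure will be utilized". It adds: "The model will contain only the intercept term". The SAP repeats the specification: "The model will contain only the intercept term. The binomial distribution with logit link function will be specified". No other interval is named for this endpoint.

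In the primary analysis the denominator is all treated major bleeds. On unrated bleeds the SAP says: "Missing assessment will be counted as failures". Bleeds treated with another product are also failures. Two sensitivity analyses change only the unrated bleeds: one drops them, the other counts them as successes. Results are shown overall and by modality, and SAP 4.6 adds inhibitor status for PUP efficacy results.

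For inhibitor incidence the boundary case is covered. SAP 4.7.1 plans an exact CI and continues: "If zero inhibitors are observed, then a one-sided 97.5% upper confidence limit will be calculated". Protocol 11.3.3.2 has the same one-sided rule. SAP 4.13 lists generic exact-binomial code but does not assign it to bleeds, and its only GENMOD example is Poisson.

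For AsBR, the other primary efficacy endpoint, the SAP plans "The number of spontaneous bleeding episodes per year based on a Poisson model and associated 95% CI" and a prophylaxis to on-demand rate ratio from the same log-link model.

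**The concern.** An intercept-only logit model estimates log(successes/failures). With no failures, or no successes, that quantity is infinite, so the interval built around it means nothing. The plan promises a two-sided 95% CI for a primary endpoint and names a method that cannot supply one in this case. The sponsor would have to publish an uninterpretable interval or choose a replacement after seeing the data, as a deviation to be justified under SAP 4.10.

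The boundary is reachable. Major bleeds are those treated at the centre as a threat to life or limb (Protocol 8.3.2), diary-reported bleeds are excluded, the enrolment target is at least 24 PUPs, and each split shrinks the cell. The log-link Poisson model for AsBR has the same weakness in a cell with no spontaneous bleeds.

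This is separate from whether within-subject correlation is modelled at all. The interval fails at the boundary either way.

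**Working it through.** The plan states no sample size, success rate or CI width for this endpoint, so there is no figure of its own to reproduce.

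**Inputs.** Model, denominators and failure rules: SAP 4.6.1.1. Assumed, because the documents are silent: number of major bleeds n from 3 to 30, and true success probability per bleed p mainly 0.90 to 0.95.

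**1. Away from the boundary the model works.** Estimate = ln(s/f), where s and f are the successes and failures among n = s + f bleeds. SE = 1/√[n·(s/n)·(f/n)].
- 9/10: ln 9 = 2.197; SE = 1/√0.9 = 1.054; 2.197 ± 1.96 × 1.054 = 0.131 to 4.263, which back-transforms to 53.3% to 98.6% (exact: 55.5% to 99.7%).
- 4/5: 30.9% to 97.3% (exact: 28.4% to 99.5%).

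**2. At the boundary it does not.** For n/n the estimate is ln(n/0).
- Ordinary fit, 5/5: the software stopped at intercept 21.6 with SE 13,073. 21.6 ± 1.96 × 13,073 runs from about −25,600 to +25,600, that is 0% to 100%. The same interval came out for every n tried from 3 to 30.
- Clustered (GEE) fit, 6/6 in 4 clusters: intercept 23.6, SE 0.53, so 22.6 to 24.6, that is 100% to 100%. All residuals are zero, so the robust variance carries no information. With n = 3 the GEE gave no result.

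These fits were run in Python (statsmodels). What SAS GENMOD would print was not tested; the infinite estimate does not depend on software.

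**3. Exact interval for the same data.** Clopper-Pearson lower limit for n/n = 0.025^(1/n): 3/3 29%; 5/5 48%; 10/10 69%; 20/20 83%.

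**4. Chance of reaching the boundary.** P(all succeed) = p^n for independent bleeds.

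| n | p = 0.80 | p = 0.90 | p = 0.95 |
|---|---|---|---|
| 5 | 0.33 | 0.59 | 0.77 |
| 10 | 0.11 | 0.35 | 0.60 |
| 20 | 0.01 | 0.12 | 0.36 |

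- Clustering raises it. With two bleeds per boy and intra-subject correlation 0.3, P(both succeed) = p² + 0.3·p(1−p). For 10 bleeds in 5 boys: 0.837^5 = 0.41 at p = 0.90 and 0.917^5 = 0.65 at p = 0.95.
- Unrated or other-product bleeds lower it in the primary analysis. At p = 0.95 with 5% of bleeds so affected, the per-bleed probability is 0.95 × 0.95 = 0.9025, giving 0.60 (n = 5) and 0.36 (n = 10). With 10% affected it is 0.855, giving 0.46 and 0.21.

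**5. Sensitivity analyses.** Suppose one bleed is unrated and the rest succeed. The primary fit has one failure and is finite. Both sensitivity fits have none and fail, provided no bleed was treated with another product.

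**6. AsBR cell with zero bleeds.** The log rate is ln(0), so there is no finite estimate. The exact one-sided 97.5% upper limit is −ln(0.025)/person-years = 3.69/person-years.

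**The case against.** Several objections have force.

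*Likelihood.* A reader might infer that all-success is the most likely outcome. The documents do not support that. They give no expected bleed count or success rate, and 24 PUPs is a minimum (the planned-number text in SAP 3.9 still says at least 50). The major-bleed definition also lists severe bleeding and leaves room for investigator judgement. At 90% success the chance is below one half by 10 bleeds. This objection stands.

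*Trigger.* A reader might also think it enough that every rated bleed succeeds. In the primary analysis it is not, since one unrated or other-product bleed makes the estimate finite. SAP 3.5.3 and 4.11 keep inhibitor-positive boys in the Efficacy population and Protocol 5.5 permits bypassing agents for them, so other-product failures are foreseeable. This makes the overall boundary less likely. It also means that an inhibitor-positive cell could sit at 0%, where the model fails equally.

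*Small cells.* SAP 3.5.6 suppresses tables for its subgroups with 3 or fewer patients, which removes the smallest ADA and inhibitor-status cells. That rule counts patients, not bleeds, and modality is not among the subgroups listed there, so it narrows the gap without closing it.

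*Consequence.* No p values are planned (Protocol 11.3), no threshold rests on this CI, and counts and percentages are reported anyway, so a bad interval would be visible and repairable. This argues against treating the gap as critical. It does not argue for leaving the substitute to be chosen after the data are seen.

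**Conclusion.** The point holds as a gap in the stated rule, not merely as missing detail: the single method given for a primary-endpoint CI has no finite solution when all or none of the treated major bleeds in a reported cell are successes. The mechanism is certain. Its probability rests on assumptions: 0.35 to 0.77 for 5 to 10 bleeds at 90% to 95% true success, 0.12 to 0.36 for 20, and less in the primary analysis if some bleeds are unrated or treated with another product. The by-modality cells and the two sensitivity analyses are the more exposed.

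The 100% to 100% clustered interval applies only if a GEE is fitted, which neither document writes out, and it was seen in Python only. It should not be read as what the planned SAS program is known to produce.

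Should-fix, not must-fix.

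**What to change.** Add to SAP 4.6.1.1; Protocol 11.3 already defers full methods to the SAP.

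1. When all or none of the treated major bleeds in a reported cell are successes (overall, by modality or by inhibitor status; primary or sensitivity analysis), replace the model CI with the exact Clopper-Pearson interval, given as a one-sided 97.5% limit, as SAP 4.7.1 does for inhibitors.
2. State that this limit treats bleeds as independent and can be too narrow when they cluster within a boy.
3. Add a supportive per-subject exact CI: among boys with at least one treated major bleed, the proportion whose treated major bleeds were all successes. Label it as a different estimand. For example, 10/10 bleeds from 5 boys gives a lower limit of 69% per bleed and 48% per boy.
4. For any reported AsBR cell with zero spontaneous bleeds, give the exact Poisson upper limit, 3.69/person-years, in place of the log-link CI. State that the prophylaxis to on-demand rate ratio is not estimable if one modality has zero bleeds.

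Cost: a few SAP sentences and one additional PROC FREQ table. The drawbacks are a change of method at the boundary and, for the per-subject analysis, a wider interval on a different quantity. The exact limit is conservative only if bleeds are independent, so the caveat in item 2 is needed.
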